Hospital admissions involves staying at a hospital for at least one night or more for medical reasons. It includes admissions to hospital wards and overnight stays in emergency departments.

Sample size

The sample size was calculated on the basis of the primary hypothesis. A total of 1050 HCW randomized with an estimated loss to follow-up of 5%, and a mean number of days off work due to illness in the control group of 5 days (SD=5) over a 6-month period will demonstrate a reduction among BCG vaccinated of 20% for a mean absence of 4 days (80% power and alpha 0.05). The estimated loss to follow-up (5%) was based on past telephone-based surveys conducted in Mozambique and Bissau.

Assignment of interventions

Randomization

All participants who give consent for participation and who fulfil the inclusion criteria will be randomly assigned to either placebo or BCG group with a 1:1 (treatment:placebo) allocation in blocks of 4 to 6 within strata defined by gender (male/female) and occupational group (doctors/nurses/other).

Blinding

The BCG vaccine will be administered by study physicians/nurses, who are not blinded but also not involved in the data collection. Participants, data collectors and data entry clerks will be blinded to the treatment allocation. In case of serious adverse events, the participant can be unblinded after consultation with the investigator or the vaccinating physician/nurse.

When the study has ended, all participants will receive information about the intervention that they received.

Data collection

Data collection instruments include: consent form, inclusion/exclusion criteria form, baseline questionnaire, follow-up questionnaire, and end questionnaire.

Variables

The endpoint variables are described in

Table 1.

Table 1 – Definition of end-point variables

Variables	Definition	Type	Scale	Domain
Absenteeism	Refers to the total number of days absent from work due to illness	Quantitative	Numeric	In days

Variables	Definition	Type	Scale	Domain
Absenteeism for COVID-19	Refers to the number of days absent from work due to COVID-19	Quantitative	Numeric	In days
Absenteeism besides COVID-19	Refers to the number of days absent from work due to diseases /illness besides COVID-19	Quantitative	Numeric	In days
Absenteeism for infections	Refers to the number of days (unplanned) absent from work due to infections	Quantitative	Numeric	In days

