Data will be reported quantitatively. All analyses will be performed from the intention-to-treat principle. Missing data on background variables will be dealt with by multiple imputation. Final data analysis will begin when the last participant in the multicentric RCT has completed the follow-up period. The primary endpoint, work absenteeism due to illness, will be reported as the total number of sick days with standard deviation. Total days of absenteeism will be analysed using a Bayesian negative binomial regression with a fixed effect for BCG, hospital, professional category, age, enrolment week and number of average workdays per week. The brm function from the R package "brms" will be used for fitting the negative binomial model. The effect will be reported as a relative risk with 95% confidence interval (CI). Please refer to section interim analysis for type-1 error control and power.

Similar regression models will be used for secondary endpoints. Cumulative incidence outcomes will primarily be analysed using Cox Proportional Hazard Regression.

Continuous baseline characteristics will be reported as means with the standard deviation or medians with the inter-quartile range, as appropriate. Categorical baseline characteristics will be reported as count and percentage. No statistical testing for baseline characteristics will be reported.

Please refer to the Data Analysis Plan for more details.

Interim analysis

Every month, an interim analysis will be conducted for each study site and of the combined dataset. Interim analyses will start after the 200th participant has been recruited across the two sites. The primary endpoint will be analysed as described above. The Bayesian model yields a posterior distribution of the relative risk (RR). The posterior probability of the superiority hypothesis ($RR < 1$) will be calculated. If during any of the interim analyses, the posterior probability of superiority is > 0.995 , a conclusion is reached, and the trial will be stopped.

Monthly, the following secondary endpoints will be reported from the sites: hospital admissions, and deaths.

IMPLEMENTATION

Inception

The study will begin with an inception meeting to be held in Cape Verde or virtually, depending on travel and quarantine recommendations at the time. Besides administrative issues, the meeting will address:

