- The injection needle is held almost parallel to the skin surface and inserted slowly with the oblique edge pointing upwards, approx. 2 mm down into the upper skin layer.
- The needle should be visible through the epidermis at insertion.
- Vaccination should be performed slowly.
- The appearance of a pale bladder is evidence of proper injection technique.
- The injection site should be uncovered to promote healing.
- The administration of the saline solution will follow the exact same procedure.

Follow-up

Follow-up will last for 6 months (182 days). Every second week, participants will be contacted over telephone and interviewed for symptoms and absenteeism from work. By the end of follow-up, participants will be invited for another POC test for COVID-19 serology.

Figure 2 - Flowchart

In case of not answering the telephone call and questionnaire for ≥ 18 days, information on the participant will be retrieved from hospital registries for absenteeism and hospital admission registries, ICU admission and outcomes. An explicit permission for this procedure will be requested from the participant during informed consent procedures at enrolment.

Participant timeline

	Staff member	Enrolment	Follow-up	End of Follow-up
--	--------------	-----------	-----------	------------------

		(W1)	(W2 to W25)	(W26)
Consent form	Research assistant	x		
Inclusion/exclusion criteria form	Research assistant	x		
POC test for COVID antibodies	Study nurse	x		
Randomization	Study nurse	x		
Administration of intervention	Study nurse	x		
Baseline questionnaire	Research assistant	x		
Follow-up Interview	Research assistant		x	
End questionnaire	Research assistant			x

Data management

The researchers will archive the published articles and the final peer-reviewed manuscripts in an online repository before, if feasible, at the same time as, or after publication in open access mode. The researchers will also make their data available according to the Open Research Data Pilot (ORD pilot) of the Horizon 2020 program.

Study management, monitoring and quality control

The project will be led by an International Steering Committee (ISC) consisting of PIs in each of the five countries involved: [name], PI from Guinea-Bissau; [name] (international coordinator), PI from Denmark; [name], PI from Portugal; [name], PI from Cape Verde; and [name], PI from Mozambique.

Figure 3 - Organogram of management structures

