An insurance for the clinical trial participants will be contracted. This insurance provides cover for damage to research subjects through injury or death caused by the study. Participants will not be compensated for participating in this study. Damage to subjects through injury or death, caused by the study or negligence of local study investigators, is not accountable to the principle investigator.

Follow-up

Follow-up will take place every second week through telephone interview and by checking register of attendance at the worksite (where available). 6 months after recruitment, the participant will be invited to the study site for a new POC test for SARS-CoV2 antibodies and to answer an end-questionnaire. The participant will be informed of the result of the test. The participant will also be informed of the intervention he/she received.

The telephone contact information of the participant will be shared only with the research assistant responsible for doing the follow-up.

Protection of personal data

This research involves data collection and processing of sensitive personal data, tracking of participants and further processing of previously collected personal data (data on immunization).

Because the study comprises follow-up of participants after administration of the intervention, data cannot be anonymised. As so, data pertaining to participants will be stored in a locked room in the institution responsible for the RCT in each country (ICSM in Mozambique and Bandim Health Project in Guinea-Bissau) in one computer not connected to the internet and protected by a password. The password will be only known by the PI, Co-PI and the study supervisors.

Data analysis will be conducted by the IHMT. Personal data include: eligibility criteria, baseline characteristics, adverse events of intervention, work absenteeism and reasons, hospitalization.

Several investigators across the world have set up trials of BCG vaccination among health care workers. Until today, >20 trials are ongoing or in preparation.

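### The 0.995 stopping rule can fire on incomplete 182-day sick-day totals, and the documents do not settle whether follow-up continues after a stop

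*Protocol*

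**What the plan says.** The Sample size section of the protocol assumes "a mean number of days off work due to illness in the control group of 5 days (SD=5) over a 6-month period" and a 20% reduction to 4 days. The protocol's Follow-up section sets 182 days of two-weekly telephone interviews for every participant. The Ethics section adds the closing visit: "6 months after recruitment, the participant will be invited to the study site for a new POC test for SARS-CoV2 antibodies".

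The Interim analysis section says "Every month, an interim analysis will be conducted for each study site and of the combined dataset" and "Interim analyses will start after the 200th participant has been recruited across the two sites". The trigger is a recruitment count, and no minimum follow-up is attached to a look. On the outcome it says "The primary endpoint will be analysed as described above", that is, with the same Bayesian negative binomial model. The model terms are BCG, hospital, profession, age, enrolment week and workdays per week; no offset for days observed is listed. When the posterior probability that RR < 1 passes 0.995, "a conclusion is reached, and the trial will be stopped".

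Other text bears on what happens next:

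- Protocol, Data analysis: "Final data analysis will begin when the last participant in the multicentric RCT has completed the follow-up period". The SAP's Statistical analysis section repeats this.
- SAP 6.1 gives an alternative start for the combined analysis: after day 182 of the study.
- SAP 3 calls the study adaptive and makes the final length of follow-up depend on observed absenteeism, its variation and the true effect.
- The SAP's Statistical analysis section provides for monthly reports to the DSMB by randomised group but gives no stopping threshold.
- The meta-analysis text just before the protocol's Safety heading says that after a first significant result in any of the trials, the others are pooled. The recommendation is to continue all trials if the effect is not confirmed.
- Protocol, Blinding: participants learn their allocation once the study has ended.

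**The concern.** The effect of interest is defined over 6 months, but the rule that can settle the question counts recruits, not follow-up. A look soon after the 200th recruitment estimates the effect over the first weeks after injection. If that look crosses the threshold, it is described as the conclusion.

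Whether this matters depends on what a stop means. If it ends enrolment only, the 182-day result still arrives. If it also ends follow-up, the later sick days are never collected, and participants not yet at month 6 miss the closing antibody test. Telling participants their allocation could also follow, because disclosure is tied to the end of the study; any absence reported after that would no longer be blinded. Two people applying the documents in good faith could do either.

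**Working it through.** **Inputs.** From the documents: N = 1050, 1:1; control mean 5, SD 5; 20% reduction; 182 days; looks monthly from the 200th recruit; threshold 0.995. Assumed, because not given: uniform accrual over A months, and a flat prior, under which P(RR < 1) > 0.995 is about z > 2.576.

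**The plan's own figure.** n per arm = 2(1.960 + 0.842)² × 5² / 1² = 392.4, so 393; total 786; 786/0.95 gives 828 after 5% loss. The stated 1050 is larger and has about 88.5% power after that loss. SAP 3 explains it as three sites of 350. This does not affect the present point.

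**Step 1: when the looks fall.** The 200th recruit comes at A × 200/1050 months, and mean follow-up then is half of that. During accrual the share of enrolled participants at day 182 is (t − 6)/t at month t; after accrual it is (t − 6)/A. Negative values count as 0.

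| Accrual (months) | Day of 200th recruit | Mean follow-up then (days) | Looks with nobody at day 182 | Month when half are complete |
|---|---|---|---|---|
| 3 | 17 | 9 | 6 of 9 | 7.5 |
| 6 | 35 | 17 | 5 of 11 | 9 |
| 9 | 52 | 26 | 5 of 14 | 10.5 |
| 12 | 69 | 35 | 4 of 16 | 12 |
| 18 | 104 | 52 | 3 of 21 | 12 |
| 24 | 139 | 69 | 2 of 26 | 12 |

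The first look has no completed outcome if 200 are recruited within 6 months: 200/6 = 33.3 per month, or A below 1050/33.3 = 31.5 months. With slower accrual, some participants have completed by then.

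**Step 2: why an early crossing is likely, by hand.** Mean 5 and SD 5 give negative binomial k from 25 = 5 + 25/k, so k = 1.25 and 1/k = 0.8. The log effect is ln(1/0.80) = 0.223.

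- Complete data: variance = [(1/5 + 0.8) + (1/4 + 0.8)]/525 = 0.00390; SE 0.0625; expected z = 3.57; chance of z > 2.576 is Φ(0.99), about 84%, at one look.
- Accrual over 6 months, look on the day recruitment ends: follow-up is uniform on 0 to 6 months, so mean days are 2.5 and 2.0, and the between-person term is multiplied by E(x²)/E(x)² = 4/3. Variance = [(1/2.5 + 1.067) + (1/2 + 1.067)]/525 = 0.00578; SE 0.0760; z = 2.94; chance Φ(0.36), about 64%. Nobody has reached day 182.

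Person-to-person variation dominates, so half the follow-up carries well over half the information.

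**Step 3: simulation of the whole rule.** RR 0.80 constant, combined data only, 3-day spells with gamma frailty (shape 2.5), 600 trials per setting. The estimate is the log ratio of sick days per day observed, with robust variance. Across accrual of 3 to 18 months, 85-88% of trials cross early. Shares of all trials:

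| Accrual (months) | Cross with under half at day 182 | Cross with nobody at day 182 |
|---|---|---|
| 3 | 80% | 72% |
| 6 | 79% | 44% |
| 9 | 74% | 36% |
| 12 | 69% | 22% |
| 18 | 54% | 16% |

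A separate gamma-Poisson simulation (k = 1.25) agrees. Crossings with under half complete are 0.887 × 0.94 = 83% of trials at 6 months' accrual, 0.883 × 0.84 = 74% at 12, and 0.875 × 0.47 = 41% at 24.

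**Step 4: effect on the estimate.** With a constant effect, the median RR at the stop is 0.76-0.77, against 0.79 when the same trials are followed to day 182. As an illustration only, suppose RR 0.70 for 60 days and then 1.00; the true 182-day RR is (60 × 0.70 + 122)/182 = 0.90. For accrual of 3 to 12 months, two runs had 44-72% of trials stopping early with a median RR of 0.63-0.68, against 0.86-0.88 in the same trials completed.

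**The case against.** The strongest reply is that the protocol already says the final analysis waits for the last participant, and the SAP repeats it. The 182-day follow-up and month-6 visit carry no exception, and the intervention is a single injection at entry, so stopping can fairly mean that enrolment ends. This stands against any claim that follow-up would certainly be cut. It does not resolve the matter: the waiting sentence does not mention a stop, while SAP 3 and SAP 6.1 allow a shorter or differently timed end.

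It can also be said that early looks are deliberate, so that policy-makers are informed during the pandemic, and that variable follow-up is a declared adaptive feature. The outcome definitions themselves name no 182-day window; it comes from the sample-size and follow-up text. That is fair, but it is a further reason to state which window the primary result covers.

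On bias, randomisation balances follow-up between arms, and enrolment week at a given look largely tracks elapsed time. The missing offset is therefore a smaller matter. No covariate recovers days that were not collected, but with a constant effect little is lost. The protocol's background expects the vaccine's effects to last at least a year, which argues against the waning illustration. The simulations also omit enrolment week and assume a flat prior that the plan does not state.

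Losing the antibody test should not be pressed hard; the protocol's risk text says serology is not central to the main objective.

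Finally, continuing follow-up after a superiority signal has to be squared with the meta-analysis text, under which a confirmed effect leads to a recommendation to offer BCG or stop trials. That stands, and it belongs in the reconciliation.

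**Conclusion.** The point holds as a gap in the stopping rule. As written, the rule can settle a 6-month question on mostly incomplete totals, and the available text does not say what happens to participants still in follow-up. If RR is 0.80 and accrual takes 3 to 12 months, an early crossing is the expected path (about 85-88% of trials). In roughly 70-80% of all trials it comes with fewer than half of those enrolled at day 182. These figures rest on uniform accrual, a flat prior and looks at the combined data only.

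Three stronger readings are tempting and not supported:

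- That nobody can have reached day 182 when the looks begin. This needs accrual above about 33 per month, which the documents do not give. Inclusions began in Guinea-Bissau on 3 December 2020 and Mozambique's national approval came 98 days later, so slow early accrual cannot be excluded. It also describes early looks only.
- That the primary outcome would never be completed for most participants. This needs an early crossing and a stop that also ends follow-up.
- That the reported effect would be badly wrong. Under a constant effect it is about 0.77 against 0.79; a large distortion needs an effect that changes over follow-up, which is an assumption.

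Part of the management and monitoring section, and the opening of the SAP, were not in the text examined. The sponsor should check whether they address follow-up after a stop. A change should be made, but the defect is not fatal.

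**What to change.** In the protocol's Interim analysis section, replace the stop sentence with three statements:

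1. Crossing 0.995 closes recruitment and is reported to the DSMB at once.
2. Participants already randomised continue the planned calls and month-6 visit to day 182.
3. The primary result is the relative risk on completed 182-day follow-up; any interim relative risk is labelled as covering the follow-up observed so far.

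At each look, report the number and share who have reached day 182, and include log(days observed) as an offset. Carry the same rule into the SAP, which has no threshold at present.

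Then reconcile it with the final-analysis timing (protocol Data analysis; SAP Statistical analysis and 6.1), the variable follow-up in SAP 3, the disclosure of allocation when the study has ended, and the meta-analysis recommendation. How a crossing should bear on those last two is for the sponsor and DSMB to settle; the documents need only say it once and consistently.

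The cost is a few sentences of protocol and SAP text. The calls and the visit are already planned for each participant, and the early signal is kept. The real downside is that the definitive 6-month estimate comes up to 6 months after a crossing.

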- The injection needle is held almost parallel to the skin surface and inserted slowly with the oblique edge pointing upwards, approx. 2 mm down into the upper skin layer.
- The needle should be visible through the epidermis at insertion.
- Vaccination should be performed slowly.
- The appearance of a pale bladder is evidence of proper injection technique.
- The injection site should be uncovered to promote healing.
- The administration of the saline solution will follow the exact same procedure.

Follow-up

Follow-up will last for 6 months (182 days). Every second week, participants will be contacted over telephone and interviewed for symptoms and absenteeism from work. By the end of follow-up, participants will be invited for another POC test for COVID-19 serology.

Figure 2 - Flowchart

In case of not answering the telephone call and questionnaire for ≥ 18 days, information on the participant will be retrieved from hospital registries for absenteeism and hospital admission registries, ICU admission and outcomes. An explicit permission for this procedure will be requested from the participant during informed consent procedures at enrolment.

Participant timeline

	Staff member	Enrolment	Follow-up	End of Follow-up
--	--------------	-----------	-----------	------------------

		(W1)	(W2 to W25)	(W26)
Consent form	Research assistant	x		
Inclusion/exclusion criteria form	Research assistant	x		
POC test for COVID antibodies	Study nurse	x		
Randomization	Study nurse	x		
Administration of intervention	Study nurse	x		
Baseline questionnaire	Research assistant	x		
Follow-up Interview	Research assistant		x	
End questionnaire	Research assistant			x

Data management

The researchers will archive the published articles and the final peer-reviewed manuscripts in an online repository before, if feasible, at the same time as, or after publication in open access mode. The researchers will also make their data available according to the Open Research Data Pilot (ORD pilot) of the Horizon 2020 program.

Study management, monitoring and quality control

The project will be led by an International Steering Committee (ISC) consisting of PIs in each of the five countries involved: [name], PI from Guinea-Bissau; [name] (international coordinator), PI from Denmark; [name], PI from Portugal; [name], PI from Cape Verde; and [name], PI from Mozambique.

Figure 3 - Organogram of management structures

- Negative effect of the intervention - negative BCG effect on COVID cannot be excluded. It is reassuring that other trials are already ongoing and are likely to detect if BCG, against all indications, should have a harmful effect in HCW, before we have enrolled a lot of participants. Hence, we would limit any harm of participants. BCG has been used for 100 years, and it is considered a very safe vaccine. We have no reason to believe that it causes harm, rather the contrary.
- Lack of clinical research experience is variable among sites and unsatisfactory compliance with requirements for data collection – the workplan contemplates: training of researchers and data collectors; pre-testing data collection tools, repeat 10% of data collection interviews by different interviewer, data entry from early on with ongoing validation. Both Mozambique and Guinea-Bissau have well established, experienced cadres of field research workers.
- Study sites with insufficient staff to perform all tasks required - Staff will either be hospital-based or working from home. Quarantine is not likely to affect health workers unless they are infected or symptomatic. That is precisely the main outcome we want to study. Collaborators doing phone calls for follow-up will be working from home/project offices.
- Hospital staff lacks interest in participating in trial - The participating hospitals anticipate having enough eligible participants between them. Should we face a situation where we cannot recruit the anticipated 1050 participants, other hospitals expressed interest in participating, but were not able to confirm participation before the grant deadline.
- Enrolment is too slow - Good management and monitoring of recruitment and follow-up.
- Recruitment is too fast and outstrips capacity of data collection team - Good management and monitoring of recruitment and follow-up.
- High volumes of data queries and re-queries - Once again good data management and monitoring.
- Staff carrying out follow-up leaves the project and needs to be replaced without losing efficiency - Both Mozambique and Guinea-Bissau have well established, experienced cadres of field research workers.
- Limited capacity for COVID-testing - If point-of-care tests are not available, we may have to collect capillary blood samples for later serology. This analysis is not central for the main objective of the RCT (absenteeism).
- Ensuring vaccine supply - We will procure vaccines locally, rather than relying on flying in vaccines specifically for the trial. This may give variability in vaccine type available (supply can be from several UNICEF-pre-qualified producers). However, in the current situation with limited shipping possibilities for research, we find this the best, pragmatic solution. If producers are different in the different sites, this will be noted, and we will scrutinize data for signs of differences in effect by producer. Essentially, this trial will address the research question of relevance for Africa now: can we use the BCG available to mitigate the pandemic.

Quality management

Quality management activities include recruitment of a Data Safety and Monitoring Board (DSMB), who are actively involved in the project, approving the quality of the project outputs, including deliverables and dissemination, and supporting the consortium in key decisions taken within the project, while maintaining their independence. Furthermore, each site will recruit an internal monitor, who will conduct at least two monitoring visits during the conduct of the trial.

ETHICS

The protocol for this study follows standard clinical trials ethical approval procedures for each country. In Mozambique, the study protocol was first approved by the CISM Committee for Bioethics in Health on the 26th of October 2021, approval number CIBS-CISM/079/2020. Approval by the National Committee on Bioethics in Health (Comité Nacional de Bioética para a Saúde), was given on March 11 2021 with approval number Ref: 115/CNBS/21. A protocol amendment regarding changes in inclusion criteria was approved on June 21, 2021 with approval number Ref: 347/CNBS/21. In Guinea-Bissau, the study protocol was approved by the Ethics Committee for Research (Comité Nacional de Ética na Saúde) on November 3 2020 with approval number 119/CNES/INASA/2020.

In Denmark, the study protocol was given consultative approval by the National Ethics Committee on November 2, 2020, approval number 2015556. In Portugal and Denmark, no local ethical approval is required as long as the study protocol is approved by the Ethics Committees of the countries where the study is to be conducted.

Ethical approval and legal documentation will be kept by the PI of the respective country.

Recruitment, inclusion and exclusion criteria and informed consent procedures.

The RCT involves healthy, volunteer human participants able to give informed consent to participate in an interventional trial consisting in the intradermal administration of BCG vaccine standard dose or placebo (saline).

The participants of this research will be health care workers defined as nurses, physicians and other health workers, including students and auxiliary staff.

Prior to the initiation of the trial, the hospital director will inform the department heads about the trial. Each department head will be provided with written material about the trial, its objectives and the practicalities. A telephone number will be provided, to which HCW can address potential questions. After a week (where presumably all staff has rotated and been informed about the upcoming trial), inclusion dates will be arranged with the department heads and communicated to staff. To avoid queuing and to ensure privacy, staff interested in participating will be asked to come one-by-one for enrolment. Whenever possible, a separate cabinet will be allocated to the study, in each study site to keep the HCW privacy.

All HCW who are 18 or older that present themselves to inclusion sites will be considered as potential participants. Those with known allergy to (components of) BCG or serious adverse events to prior BCG administration; known previous, active or latent infection with *Mycobacterium tuberculosis* or other mycobacterial species; fever (>38 C) within the past 24 hours; suspicion of active viral or bacterial infection; pregnancy; and severe immunocompromised subjects; active solid or non-solid malignancy or lymphoma within the prior two years; or with contraindication for live attenuated vaccine administration, will be excluded.

Participants will be asked about their HIV status and a HIV test will be performed before enrolment. Because they are HCW, we believe that most of them are aware of their HIV status, especially in high prevalence settings as is the case of Mozambique. Participants who report that they are HIV-positive and those that test positive with the point-of-care HIV test will be excluded from the study; the latter will be referred for confirmatory testing.

Eligible participants will be invited to participate in the study after being informed thoroughly about the intervention and having been given the opportunity to discuss the main features of the study with the research team and having the possibility to ask questions. The discussion will include the aims, methods and implications of the research, the nature of the participation, potential benefits, risks or discomfort that might ensue as well as the voluntary nature of their participation and the right to withdraw from the study.

After information of the main features of the study, participants will be asked to sign the information sheets, containing all information in writing plus the e-mail and telephonic contacts of the research team, procedures to withdraw from the study and informed consent. The informed consent will comprise 1) consent to have either BCG or saline water administered by intradermal injection; 2) consent to collect personal data as determined in the study protocol; 3) consent to do POC testing for SARS-CoV2 antibodies at the beginning and end of the study; and 4) consent to be contacted through mobile calls biweekly during follow-up procedures conducted by the research team.

Each participant will be given a copy of the signed informed consent and information sheets and a second copy will be kept by the research team in each study site. Informed consent for all study sites will be kept by the country research team in a locked room where only research team personnel will have access.

Risk assessment for intervention

Based on previous experience and randomized controlled trials in adult and elderly individuals, the risks of BCG vaccination are considered low. It is common and not treatment-demanding that, following BCG vaccination, redness, swelling and ulceration of the skin where the vaccine is given will occur. There may be swollen lymph nodes in the area some weeks after the vaccine is given, and in the longer term, a small ~5 mm diameter scar will appear where the vaccine was given. In case these appear, we will follow the recommendations of the National Immunization plan. Severe but very rare side effects are injection site abscesses, BCG lymphadenitis, disseminated BCG diseases, osteitis, osteomyelitis, anaphylaxis, formation of keloid/lupoid and suppurative lymphadenitis. In case these adverse events occur, the participant will be provided with medical assistance.

An insurance for the clinical trial participants will be contracted. This insurance provides cover for damage to research subjects through injury or death caused by the study. Participants will not be compensated for participating in this study. Damage to subjects through injury or death, caused by the study or negligence of local study investigators, is not accountable to the principle investigator.

Follow-up

Follow-up will take place every second week through telephone interview and by checking register of attendance at the worksite (where available). 6 months after recruitment, the participant will be invited to the study site for a new POC test for SARS-CoV2 antibodies and to answer an end-questionnaire. The participant will be informed of the result of the test. The participant will also be informed of the intervention he/she received.

The telephone contact information of the participant will be shared only with the research assistant responsible for doing the follow-up.

Protection of personal data

This research involves data collection and processing of sensitive personal data, tracking of participants and further processing of previously collected personal data (data on immunization).

Because the study comprises follow-up of participants after administration of the intervention, data cannot be anonymised. As so, data pertaining to participants will be stored in a locked room in the institution responsible for the RCT in each country (ICSM in Mozambique and Bandim Health Project in Guinea-Bissau) in one computer not connected to the internet and protected by a password. The password will be only known by the PI, Co-PI and the study supervisors.

Data analysis will be conducted by the IHMT. Personal data include: eligibility criteria, baseline characteristics, adverse events of intervention, work absenteeism and reasons, hospitalization.

Several investigators across the world have set up trials of BCG vaccination among health care workers. Until today, >20 trials are ongoing or in preparation.

Spearheaded by the Dutch group, a platform is now being established for a meta-analysis to be done immediately (i.e. within one week) after the first trial yields a significant result. The meta-analysis will include all ongoing trials except for the one yielding the significant result. If the meta-analysis confirms the effect (i.e. statistically significant difference at a two-sided p-value < 0.05) the recommendation will be to offer BCG to HCW or to stop trials. If it is not confirmed, the recommendation will be to continue all trials. The result of the interim analysis will be made public to inform health authorities.

A Data Transfer Agreement has been established to allow anonymous sharing of our data to contribute to this meta-analysis.

Safety

Intervention consist of intradermal administration of a standard dose of BCG vaccine or placebo (saline). Based on previous experience and randomized controlled trials in adult and elderly individuals, the risks of BCG vaccination are considered low. It is common and not treatment-demanding that, following BCG vaccination, redness, swelling and ulceration of the skin where the vaccine is given will occur. There may be swollen lymph nodes in the area some weeks after the vaccine is given, and in the longer term, a small ~5 mm diameter scar will appear where the vaccine was given.

Severe but very rare side effects are injection site abscesses, BCG lymphadenitis (simple or suppurative, disseminated BCG disease, osteitis, osteomyelitis, anaphylaxis, formation of keloid/lupoid. They are so rare that it would be unlikely with cases in the present trial of 1050 participants, but we will specifically enquire about adverse events at the weekly interviews and in the end questionnaire. In the case of adverse events they will be reported to the vaccine producer and the patient will be receive treatment.

Temporary halt for reasons of subject safety: In accordance to section 10, subsection 4, of the Medical Research Involving Human Subjects Act (WMO), the sponsor will suspend the study if there is sufficient ground that continuation of the study will jeopardize subject health or safety.

The sponsor will notify the EC without undue delay of a temporary halt including the reason for such an action. The study will be suspended pending a further positive decision by the EC and the DKMA. The investigator will take care that all subjects are kept informed.

Adverse events (AEs): defined as any undesirable experience occurring to a subject during the study, whether or not considered related to the investigational product, the placebo or the trial procedures, will be biweekly assessed during the mobile phone interviews. All adverse events will be reported to the relevant authorities according to existing national notification procedures.

Serious adverse events (SAEs) is any untoward medical occurrence or effect that results in death, is life threatening or requires hospitalization or prolongation of existing inpatients' hospitalization, results in persistent or significant disability or incapacity, is a congenital anomaly or birth defect or any other important medical event due to the intervention based upon appropriate judgement by the investigator. An elective hospital admission will not be considered as a serious adverse event.

Participants will be asked about the occurrence of SAE's biweekly in the questionnaire. In case of a SAE, dependent on the symptoms of the participant, he/she will be contacted by the investigator and if necessary, admitted to the hospital. The condition of the participant will be evaluated by the investigator, who can decide to un-blind if deemed necessary.

The investigator will notify sponsor and DSMB within 24 hours after first knowledge of any SAEs, in order for DSMB and sponsor to assess whether it is a suspected unexpected serious adverse reactions (SUSAR).

Unexpected adverse reactions are SUSARs if the event is serious, if there is a certain degree of probability that the event is a harmful and an undesirable reaction to the medicinal product under investigation, regardless of the administered dose and it is unexpected, that is to say, the nature and severity of the adverse reaction is not in agreement with the product information as recorded in the summary product characteristics.

The investigator and the sponsor will report to the EC and competent national authorities.

Beneficence

